6.2.2 Blinding procedures

Not applicable. The study is not blinded.

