6.2.3 Other methods of minimising bias

Patients will be randomized into two different groups. We will avoid age bias by choosing only patients from 18 to 55 years. Neutral recruiting will take place at USZ Allergy Unit.

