9.2.1.3 Analysis of T-cell activation by flow cytometry

PBMCs are also analyzed by flow cytometry after allergen-restimulation in vitro. Briefly, the cells are typically cultured 18-20h in the presence of grass pollen allergens, the last 4-6 hours of the incubation, the compound brefeldin A is added to prevent the golgii apparatus to release newly produced proteins. Then, the cell are stained for with fluorescent antibodies to detect lymphocytes, lymphocyte activation surface proteins. The cell are then fixed, permeabilised and stained to detect intracellular transcription factors such as Foxp3, STAT-1 and STAT-3 and STAT-6 as well as intracellular cytokines such as IL-4, IL-10 and IFN-gamma. The exact cytokines may depend on the result from the above-mentioned ELISA

studies. The cells are acquired on a BD LSR-Fortessa Cell analyzer and the data analyzed using FlowJo LCC software.

[figure not shown]

Figure 4. Patient flow chart illustrating study visits with timing, interventions, and assessments for patients treated by ILIT or SCIT for grass pollen-mediated allergic rhinoconjunctivitis.

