12.1 Data handling and record keeping / archiving

12.1.1 Case Report Forms

Study data is recorded in Case Report Forms on paper (pCRF). Data entry will be done by the investigators who are responsible for the correctness of the data. If a person is enrolled to participate in the study, the personal record will be encoded, and the person given a randomization number. For each enrolled study participant a pCRF is maintained. All patient information and test results are recorded in the CRF. Only the participant number and the year of birth will be entered in the pCRF. The encryption process used for the pCRF are in accordance with Swiss guidelines for encryption. Hence, only the investigators and authorized persons have access to data.

The pCRFs are kept current to reflect subject status at each phase during the course of study. The investigators at the site are responsible for pCRF entries and have to sign their entries with initials and date of the entry according the specifications of the pCRF.

The informed consent will be obtained in wet ink during the screening visit and then uploaded to the clinical information system (KISIM) and filed into the TMF for recordkeeping.

Data transfer in excel tables for statistical evaluation is checked by double data entry. A printout of the excel sheet is added to the study documents and every data change in the electronic data should be assigned a new printout.

The randomization list will be stored electronically as a series of files labelled with the participant number that contains information on the randomization, with password-protected, logged access and an audit trail that will be stored electronically for 15 years. As this is an open-label trial, any physician can access the randomization list, and request details of the allocation of an individual patient.

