12.5 Confidentiality, Data Protection

Health-related personal data captured during this project from participants are strictly confidential and disclosure to third parties is prohibited. Coding will safeguard participants' confidentiality.

The electronic case report forms (CRFs) will be entered into an excel-based database. Confidentiality will be ensured by entering only coded data into the analysis set. The coded data will be password-protected and accessible to the sponsor, the medical investigators and the project researchers. The statistician will obtain copies of the Excel database after the data entry has been completed. Coded research data are not considered part of the essential documents and will be stored on a central data server at the USZ with restricted access: \\fs-group\der_forschungen\DER_FL_Immunotherapie

The code for data generated at USZ is kept with the sponsor.

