12.6 Storage of biological material and related health data

Data from this trial will be stored for 10 years in electronic form after completion of the trial. The collected blood and FNA samples are to be used and analysed exclusively in the current study. No material or data transfer to other or future projects are foreseen. The collected blood samples and FNA in this study

is not identified by participant name but by a unique participant number and is appropriately stored in a restricted area only accessible to the authorized personnel.

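### Samples carry participant numbers, but no rule keeps treatment arm or node side from the people who analyse the flow and mass cytometry data

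*Combined protocol and SAP*

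**What the plan says.** All places are in the combined protocol and SAP.

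- **Blinding.** Section 6.2.2 reads "Not applicable. The study is not blinded", and 6.3 repeats this for code breaking. Section 6.2.3, on other ways of limiting bias, mentions randomisation, an age restriction ("We will avoid age bias by choosing only patients from 18 to 55 years") and neutral recruitment. Masked laboratory work is not mentioned.
- **Sample labels.** Section 12.6 says that stored material "is not identified by participant name but by a unique participant number".
- **Allocation files.** Section 12.1.1: "The randomization list will be stored electronically as a series of files labelled with the participant number". The same sentence adds password protection, logged access and an audit trail. The next says "As this is an open-label trial, any physician can access the randomization list, and request details of the allocation of an individual patient".
- **Access to coded data.** Section 12.5 opens the coded data to the sponsor, the medical investigators and the project researchers, and states: "The code for data generated at USZ is kept with the sponsor".
- **Readouts.** Serum antibodies and tryptase are measured by ImmunoCAP (9.2.1.1). Cytokines are measured by ELISA on a plate reader, and ELISPOT on an automated reader (9.2.1.2). For flow cytometry, 9.2.1.3 says "the data analyzed using FlowJo LCC software" and adds that the cytokines stained may depend on the ELISA results. Mass cytometry samples are barcoded by patient, pooled, and explored with PCA, t-SNE and UMAP (9.2.1.4).
- **Analysis.** Section 11.4 makes the investigators and an appointed statistician jointly responsible, and plans comparative testing of SCIT versus ILIT.

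**The concern.** The trial's outcomes are laboratory readouts of cell composition and function (5.1), so most of the protection against reader expectation has to come from how samples are read. Flow gating and the naming of cell populations normally involve judgement, and 9.2.1.3 and 9.2.1.4 give neither a gating plan nor predefined cluster labels. The choice of cytokines for flow is left open until ELISA results are in. An analyst who knows the arm, or which of the two nodes was injected, can be influenced at each of these steps without noticing.

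The rationale also has a direction. Section 3.1 expects more efficient allergen delivery with ILIT, and under both theories in 4.1 SCIT is the weaker or less efficient route. No single primary endpoint is defined (4.2), so a modest systematic shift in some readouts could surface as one of the reported hallmarks. Section 3.1 intends the results to inform larger follow-up studies, so a biased hallmark would carry forward.

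**Working it through.** **Step 1: does the existing coding hide allocation?**

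| Question | Source | Answer |
|---|---|---|
| What is on the tube? | 12.6 | Participant number |
| What labels the allocation files? | 12.1.1 | Participant number |
| Who may consult the list? | 12.1.1 | Any physician; access is logged |
| Who sees coded data? | 12.5 | Sponsor, medical investigators, project researchers |
| Who analyses? | 11.4 | Investigators and a statistician |
| Is there a rule withholding arm or node side from readers? | 6.2.2, 6.2.3, 9.2.1.1 to 9.2.1.4, 11.4 | None found |

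The tube number is thus the look-up key to the arm for anyone with access to the list. The number itself does not reveal the arm, and the documents do not say how the two aspirates from one patient are told apart. Concealment is therefore not assured; it has not been shown to fail.

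**Step 2: which readouts are exposed?** ImmunoCAP, ELISA and ELISPOT are instrument-read, so exposure is low. Flow cytometry and mass cytometry are exposed through gating and population labelling. These manual steps are inferred from the methods named; the protocol does not describe them. The choice of cytokines after ELISA is stated in 9.2.1.3.

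**Step 3: how sensitive would a comparison be?** The plan states no alpha, power or effect size (11.2 gives no sample size calculation), so there is no figure of its own to reproduce. What follows is illustration only.

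Inputs from the documents: 15 per arm (7.3; the synopsis still describes three groups of 10). Aspirates and early blood are taken at 2, 6 or 24 hours (6.1).

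Assumptions: two-sided 5% t-test (for two groups equivalent to ANOVA), SD 1, no true difference, and a reader shift of b SD between arms. An equal split over the three times gives 15/3 = 5 per arm.

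Noncentrality: λ = b × √(n/2), with 2n − 2 degrees of freedom. The rejection rate is P(|T| > t₀.₉₇₅) for T noncentral t.

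| n per arm | df | critical t | b | λ | Rejection rate |
|---|---|---|---|---|---|
| 15 | 28 | 2.048 | 0.2 | 0.548 | 8.3% |
| 15 | 28 | 2.048 | 0.3 | 0.822 | 12.5% |
| 15 | 28 | 2.048 | 0.5 | 1.369 | 26.2% |
| 5 | 8 | 2.306 | 0.5 | 0.791 | 10.8% |

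These are rates per readout, against a nominal 5%. They apply only to readouts open to operator judgement.

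**Step 4: size of the task.** Section 8.7 gives 2 aspirates and 4 blood collections per patient: 30 × 2 = 60 and 30 × 4 = 120, together 180. Aspirates and blood cells are frozen before analysis (8.2.1.2, 8.2.1.3), so recoding can be done before reading.

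**The case against.** The strongest reply is that this is an open-label, descriptive pilot. Section 11.1 says it does not set out to confirm a particular difference, samples are already coded, access to the list is logged, and several assays are read by machine. The mass cytometry collaboration is with a separate institute (14.2.1), and nothing says its staff see the allocation. Written SOPs exist (section 12) that a reader of the protocol cannot see.

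Much of this stands, and it rules out some stronger readings that a reader might infer:

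- **That every readout is subjective, including counting.** Not supported: ImmunoCAP, ELISA and ELISPOT use instruments.
- **That samples are uncoded, or that the code openly shows arm and side.** Not supported: the number is there and does not itself reveal either. What is missing is a rule separating it from allocation.
- **That bias towards ILIT will occur, at a known rate.** Not supported: the documents give no shift, and the percentages rest wholly on assumed ones.
- **That masking is free.** Not supported: recoding and key-keeping take work.

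What the reply does not remove is the absence of any masking statement. Logging records who opened the list but does not stop a reader from knowing the arm. The plan also includes comparative tests (11.4), so the pilot label does not make reader bias irrelevant.

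**Conclusion.** The point holds in a limited form. Participant-number coding protects confidentiality, but no stated rule keeps arm or node side from those who analyse flow and mass cytometry data. The exposed steps are gating, population labelling and the cytokine choice after ELISA; the instrument-read assays are less exposed.

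The size of any bias is unknown. The 8% to 26% range depends on an assumed shift, an assumed test level and the full 15 versus 15 comparison. With about 5 versus 5 at each sampling time, the upper figure falls to about 11%. It also rests on the inference that gating and labelling involve operator judgement, which is usual but not written in the protocol. This is a cheap improvement of moderate severity for a descriptive pilot; it does not invalidate the design.

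**What to change.** Three changes:

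1. **Section 6.2.2.** State that injections are open label, but that laboratory staff and cytometry analysts work without access to the randomisation list until their readouts are final. Align the access sentence in 12.1.1 with this.
2. **Section 12.6.** Relabel samples with study codes that hide arm and node side, with the key held outside the laboratory. Tubes from one patient must stay linkable, because 9.2.1.4 barcodes by patient. A random patient code with a random tube suffix would do this.
3. **Sections 9.2.1.3 and 9.2.1.4.** Fix and date the gating strategy, marker panel (including the cytokines chosen after ELISA) and cluster labels before allocation is linked. If the cytokine choice must use ELISA data, make it on results not split by arm.

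The cost is low but not zero: recoding about 180 samples (more labels where blood is aliquoted), keeping a key, and waiting for plots by arm until the code is released. Sample size, visits and patient care do not change.

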6.2.3 Other methods of minimising bias

Patients will be randomized into two different groups. We will avoid age bias by choosing only patients from 18 to 55 years. Neutral recruiting will take place at USZ Allergy Unit.

6.3 Unblinding Procedures (Code break)

Not applicable. The study is not blinded.

7. STUDY POPULATION

7.1 Eligibility criteria

Participants fulfilling all of the following inclusion criteria are eligible for the study:

- Patients who have seasonal grass-pollen-induced rhinoconjunctivitis as confirmed by patient history and type-1-sensitization to grass-pollen in skin and/or serum
- Patients that undergo pre-seasonal short-term scheme with Polvac™ SCIT at the USZ Allergy Unit in autumn and winter 2023 for treatment of allergic rhinoconjunctivitis.
- Informed Consent as documented by signature.
- Patients are between 18 and 55 years of age when they sign the informed consent.

The presence of any one of the following exclusion criteria will disqualify the patient from participating the study:

Allergy related exclusion criteria:

- Known or suspected allergy to additives to the study product
- Known intolerance or allergy to phenol
- Planned depot steroid injection for treatment of allergic rhinoconjunctivitis
- Uncontrolled asthma or severe asthma with post bronchodilator $FEV1 < 70\%$, decided by the investigator
- Pulmonary disease with post bronchodilator $FEV1 < 70\%$ of predicted
- Pulmonary disease, perennial or seasonal, with daily use of more than 800 microgram inhaled budesonide/day (or equivalent)
- Treatment with omalizumab or other biologics for allergy, AD, urticaria or asthma.
- Allergic reaction within the last 4 days or anaphylaxis within last month before planned ILIT or SCIT injection.

Exclusion criteria based on serious comorbidities as judged by the recruiting physician:

- Autoimmune or collagen disease
- Disease or conditions rendering the treatment of anaphylactic reactions difficult (symptomatic coronary heart diseases, severe arterial hypertension, and treatment with beta-blockers)
- Concomitant infection with fever or other signs/symptoms of an acute or chronic infection at treatment visit
- Vaccination of any kind two weeks before or after the ILIT or SCIT injections.
- Known cardiovascular disease, i.e., not even NYHA class I.
- Use of ACE-blockers.
- Recent or on-going hepatic or renal disease
- Any malignant disease
- Conspicuous lymph node size or morphology
- Immuno- or chemotherapy during the last 15 years.
- Increased bleeding tendency
- Any other than study medication with an effect of interfering with the immune response
- Chronic obstructive or restrictive lung disease
- Skin diseases with barrier defect in the inguinal areas
- Alcohol or drug abuse
- Women who are pregnant and breast feeding

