Objective(s):	The study seeks primarily to determine hallmarks in immunological responses (analysis of inflammatory cell and proteins) in lymph nodes and in peripheral blood after allergen ILIT and SCIT.
Outcome(s):	
 1) Fine needle aspiration (FNA) material of lymph node tissue at baseline and 2 or 6 or 24 hours after allergen ILIT or SCIT will be evaluated for changes in cell populations and cell functions. 2) Immunological changes (analysis of cell populations and functions ex vivo and in vitro) in peripheral blood at baseline, after 2 or 6 or 24 hours, after 7 days and after 28 days of allergen ILIT or SCIT.

Study design:	
This is a prospective, comparative, clinical study. We will recruit 30 grass-pollen allergic patients undergoing pre-seasonal short-term SCIT scheme with Polvac™ Grass+Rye at the USZ Allergy Unit. 4 weeks after last SCIT injection and after reaching maintenance SCIT dose (2000 U), the patients will receive an additional allergen injection as part of the study. Patients will be randomized into the 3 different groups with 10 participants per group. Patients will receive a single ultrasound-guided injection with Polvac™ Grass+Rye ILIT (0.1 ml, 400 U) or SCIT (0.5 ml, 2000 U).
 
FNA of lymph node tissue will be conducted at baseline and at 2, 6 or 24 hours after allergen injection. Venous blood will be sampled at baseline, after 2, 6 or 24 hours, after 7 days, and after 28 days of allergen injection.

Inclusion / Exclusion criteria:	
Included are patients between 18 and 55 years of age with grass-pollen allergy and undergoing pre-seasonal short-term-scheme Polvac™ Grass+Rye SCIT at the USZ Allergy Unit for treatment of allergic rhinoconjunctivitis.
 
Exclusion criteria are significant allergy to house dust mite or pet animal allergens, uncontrolled asthma, upper airway disease, severe pulmonary disease, recent allergic reactions, immunosuppression, cardiovascular disease, malignant disease, conspicuous lymph node size or morphology, use of ACE-blockers and any other diseases or conditions rendering the treatment of anaphylactic reactions difficult.

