3.5 Rationale for the dosage, route, regimen

We will include grass pollen allergy patients with pre-seasonal short-term and pre-seasonal injection scheme with Polvac™ SCIT at the USZ Allergy Unit (Head: [name]). After the patients have received the full cycle of SCIT (six injections) as a part of standard care, they will be randomized into one of the two study groups for one additional injection, which is to be given 4-6 weeks after the last SCIT cycle injection. Depending on the group allocation, patients will receive allergen by SCIT (or by ILIT). *Figure 2* illustrates schematically the study design and *Figure 3* shows the flow chart for the study participants.

Polvac™ Doses:

- SCIT (n=15): 0.5 ml Polvac™ (max maintenance dose, 2000 U).
- ILIT (n=15): 0.1 ml Polvac™ (400 U).

The SCIT dose is chosen as this is the recommended and standardized treatment dose for patients receiving SCIT with Polvac™ for treatment of grass pollen allergy. The ILIT dose is 1/5th of the maintenance SCIT dose. This has been safely administered in four patients treated off-label with Polvac™ at the USZ allergy in 2023 ([name] and [name], personal communication). These four patients received three injections in a dose escalating manner and with four-week intervals. The doses were 1/15th, 1/10th and finally 1/5th of the maintenance SCIT dose. An ILIT dose of 1/15th of the maintenance SCIT dose was safely administered three times in 30 patients in the aforementioned ongoing study with Polvac™ ILIT (BASEC 2021-02301).

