6. STUDY DESIGN

6.1 General study design and justification of design

This is a prospective, comparative, clinical open label pilot study. From patients with grass pollen allergy who undergo a pre-seasonal SCIT scheme with Polvac™ Grass+RyeSCIT at the USZ Allergy Unit, 30 patients will be recruited for the study that is illustrated in Figure 2.

Four to six weeks after end of SCIT treatment (at maximal maintenance dose), the patients will be randomized to one out of two treatment groups and receive one additional allergen injection. Fifteen patients will be allocated to receive another subcutaneous injection with 0.5 ml (2000 U) Polvac™

Grass+Rye. The other 15 patients will be allocated to receive an intralymphatic injection of 0.1 ml Polvac™ Grass+Rye with 400 U allergen. Both SCIT and ILIT injections are performed by ultrasound-guidance as to assure injection into the lymph node (ILIT) or 1 cm next to the lymph node (SCIT).

The FNA of lymph node tissue will be conducted at 2, 6 or 24 hours after allergen injection. At the same time, FNA of a contralateral lymph nodes will be performed as baseline. Venous blood will be sampled at all visits: at baseline as well as after 2, 6 or 24 hours, after 7 days and after 28 days of the allergen ILIT or SCIT. The FNA is performed by ultrasound-guidance.

[figure not shown]

Figure 2. Study design illustrated schematically the open-label clinical pilot study for assessment of immunological and inflammatory responses to a single ILIT or SCIT in patients receiving grass pollen immunotherapy with Polvac™ Grass+Rye.

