8. STUDY INTERVENTION

8.1 Identity of Investigational Products

Four weeks after patients have received the full cycle of SCIT with Polvac™ Grass+Rye as a part of standard care treatment, they will be randomized to receive one additional treatment.

All study participants will receive again the same allergen extract (Polvac™ Grass+Rye). Depending on the group allocation, they will receive the allergen by the subcutaneous (SCIT) or by intralymphatic (ILIT) injections.

The following Polvac™ doses are used:

- SCIT (n=15): 0.5 ml Polvac™ (2000 U).
- ILIT (n=15): 0.1 ml Polvac™ (400 U).

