8.3 Dose modifications

We already have experiences with dosing Polvac™ from an ongoing study using Polvac™ at our department (BASEC Number: 2021-02301) and with off-label use of up-dosing Polvac™. The ILIT doses used in the trial described in the current protocol is based on the experience from the past trial (133 U) and from off-label treatment of four patients in February to April 2023 (133 U, 200 U and 400 U).

We inject the study dose after patients finished a full cycle of pre-seasonal short-term SCIT scheme with Polvac™ (the patients have therefore reached and tolerated the maximal maintenance dose of 2000 U). The maximal dose in the current study will not exceed the maintenance dose for SCIT (2000 U) and will be much lower for ILIT (400 U) and should therefore be well tolerated by the study participants.

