8.4 Compliance with study intervention

Monitoring of subject compliance will not be done. We only include patients who have finished pre-seasonal SCIT with six injections at the USZ Allergy Unit. Patients who opt for SCIT are usually highly motivated because their burden of allergy-suffering is high. The effort for the patient associated with our study is relatively modest. The five personal visits include 1) screening visit (which can be combined with a SCIT injection already planned), 2) allergen injection, 3) FNA and blood samplings 2-24 hours post injection, 4) follow-up after 7 days, and 5) follow-up after 28 days. We expect that the patients will be motivated for the study, because they potentially will benefit from this one additional injection and might also benefit from future ILIT applications (such as off-label interventions).

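### The dose rationale rests partly on patients having tolerated 2000 U by SCIT, but no visible eligibility criterion requires this, and the 4-day reaction window in 7.1 cannot reach the last SCIT dose

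*Combined protocol and SAP*

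**What the plan says.** Section 8.3 (Dose modifications) argues that the study doses should be well tolerated. One ground is that the injection comes after a full pre-seasonal cycle: "the patients have therefore reached and tolerated the maximal maintenance dose of 2000 U". The other is earlier Polvac ILIT experience: 133 U in a previous trial, and 133, 200 and 400 U in four patients treated off-label. Section 3.5 adds that those four were escalated to the highest dose.

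Three places describe who qualifies on prior SCIT:

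- Section 7.1 asks only that patients undergo the short-term Polvac scheme at the unit.
- Section 8.4 goes further: "We only include patients who have finished pre-seasonal SCIT with six injections at the USZ Allergy Unit".
- The synopsis (Study design) times the study injection at "4 weeks after last SCIT injection and after reaching maintenance SCIT dose (2000 U").

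The exclusion in 7.1 that looks at past reactions reads "Allergic reaction within the last 4 days or anaphylaxis within last month before planned ILIT or SCIT injection". The synopsis lists recent allergic reactions among its exclusions without giving a window.

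On timing, 3.5 describes one additional injection, "which is to be given 4-6 weeks after the last SCIT cycle injection". Section 6.1 says "Four to six weeks after end of SCIT treatment (at maximal maintenance dose), the patients will be randomized", and 7.4 uses the same 4-6 week frame for replacements. The synopsis and 8.1 ("Four weeks after patients have received the full cycle of SCIT with" the study product) give four weeks only.

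**The concern.** Finishing six injections and reaching 2000 U show exposure, not tolerance. A patient who develops generalised hives or chest tightness after the sixth injection has still finished the cycle and still reached the dose. Section 8.3 treats completion as if it proved tolerance, and nothing visible in the eligibility section turns that inference into a requirement.

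This bears on patient safety. Section 3.8 says that patients already on immunotherapy were chosen to lower the risk of allergic side effects and to permit a higher dose. A patient who reacted systemically at the last 2000 U dose lacks the property on which that choice depends. In the SCIT arm this patient would receive the same dose again. In the ILIT arm the patient would receive 400 U directly into a node, in a single step and without ILIT escalation. Direct experience with Polvac ILIT at 400 U is four patients, all escalated to it, so SCIT tolerance carries a real share of the dose argument.

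**Working it through.** The plan gives no figure to reproduce here. The check is date arithmetic and a comparison of the text, followed by a rough sense of scale.

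**Inputs.** Gap from last SCIT dose to study injection: 4-6 weeks = 28 to 42 days, which is 42 − 28 + 1 = 15 possible gap days (3.5, 6.1, 7.4); four weeks = 28 days in the synopsis and 8.1. Look-back windows: 4 days for an allergic reaction, one month for anaphylaxis, counted back from the study injection (7.1). Participants: 30 (7.3). Reaction counts: 11 of 462 injections in 154 patients with allergic symptoms such as hives, chest tightness or a marked FEV1 fall, and 1 of 462 severe (3.7).

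**Step 1: the 4-day window.** Time from the last SCIT dose to the opening of the window = gap − 4. Shortest gap: 28 − 4 = 24 days. Longest gap: 42 − 4 = 38 days. The window therefore opens 24 to 38 days after the dose. An immediate or early delayed reaction to that dose is not captured at any permitted gap, including exactly four weeks.

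**Step 2: the one-month window for anaphylaxis at the last SCIT dose.** It is covered only if the gap is no longer than the month.

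| Month read as | Gap days covered | Gap days missed |
|---|---|---|
| 28 days | 1 of 15 (28) | 14 of 15 |
| 30 days | 3 of 15 (28-30) | 12 of 15 |
| 31 days | 4 of 15 (28-31) | 11 of 15 |

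If the gap is held to exactly four weeks, anaphylaxis is covered on every reading. Over the 4-6 week range it is missed once the gap passes about 30 to 31 days.

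**Step 3: other scheduled checks.** Table 1 ticks medical history and the inclusion/exclusion check at Visit 1 only. Visit 2 (Table 1 and 9.3.2) has a pregnancy test, peak flow before and after injection, an adverse-event and concomitant-medication tick, blood sampling and the injection. Tolerance of the SCIT doses is not a named item at either visit. Section 8.4 also describes a "screening visit (which can be combined with a SCIT injection already planned"), so a reaction to that day's dose could follow the screening interview. If a reaction does come to light, no visible criterion makes it disqualifying.

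**Step 4: scale, as an illustration only.** Rate per injection = 11/462 = 2.38%. Assuming this applies to the last SCIT dose, the expected number of reactors is 30 × 11/462 = 0.71. At an assumed 1% it is 30 × 0.01 = 0.3; at the protocol's rounded 2% it is 30 × 0.02 = 0.6. For a severe event, 30 × 1/462 = 0.065. The fit to this setting is poor: 462/154 = 3 injections per patient, whereas 3.2 describes a six-injection cycle, and 3.7 does not say that the reactions occurred at 2000 U.

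**The case against.** The strongest reply is that the 7.1 exclusion was probably meant to check the patient's acute state on the day and was never meant to certify SCIT tolerance. That is fair. The gap is a missing criterion rather than a fault in this one, but it remains a gap because 8.3 relies on the property.

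Second, tolerance is not the only support for the doses. Section 8.3 cites Polvac ILIT at 133 U and the four patients given 400 U, and 3.4 cites a report that high-dose ILIT after recent SCIT was safe. This stands and lowers the weight of the point. None of that experience is stated to include patients who had reacted to SCIT.

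Third, practice may close the gap. Section 7.2 describes an extensive interview, Visit 1 includes a medical history, and the SCIT is given at the same unit, so a reaction may well come to light and an allergist may decline the patient. Section 3.2 says that Polvac for SCIT is used as the provider describes in Appendix 001. That appendix and the SmPC (Appendix 002) are not available here and may govern dosing after a reaction. Peak flow, one hour of observation and the rescue set limit harm, although they do not select patients.

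Two stronger readings are tempting. A reader might compute 1 − (1 − 11/462)^30 = 51% and conclude that the trial will more likely than not enrol a reactor. The documents do not support that: the rate comes from three injections per patient, is not tied to 2000 U or to a sixth dose, and counts reactors rather than reactors who are then enrolled. A reader might also take the 60-day screening limit in 7.2 to mean that eligibility is settled weeks before the last SCIT dose. Section 9.3.1 limits screening to 29 days before Visit 2, and 8.4 admits only patients who have finished the cycle. The differing screening windows are a separate consistency matter.

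**Conclusion.** The point holds in a limited form. Tolerance of 2000 U is a stated premise of the dose rationale, but it is not a condition of entry in any text that can be seen. The 4-day exclusion misses a non-anaphylactic systemic reaction at the last SCIT dose at every permitted gap. The one-month exclusion misses anaphylaxis at that dose once the gap exceeds about 30 to 31 days.

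The number of patients affected is unknown. About 0 to 1 of 30 is a rough illustration that assumes the 3.7 rate carries over to the sixth injection. The date arithmetic does not depend on that rate. The conclusion assumes that the appendices contain no binding rule excluding such patients from the study injection.

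The documents do not show that a reactor would in fact be dosed, or that SCIT tolerance is the sole safety ground. This is a cheap improvement for patient safety, of minor to should-fix severity, with moderate confidence.

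**What to change.** Add one inclusion criterion to 7.1: the patient completed all six SCIT injections and received the last 2000 U dose without a systemic allergic reaction. The reaction terms already listed in 3.7 can define systemic. Because the criterion is tied to the dose and not to a number of days, it also covers anaphylaxis at that dose whatever the gap.

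Confirm it from the Allergy Unit's injection record before the Visit 2 injection, with one tick under Visit 2 in Table 1 and one line in 9.3.2. Where the sixth injection has already been given by Visit 1, check the record then, before the randomisation envelope is opened. This avoids excluding a patient after allocation in an open-label trial.

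The cost is amendment wording, one CRF line and one record check at the unit that gives the SCIT. The downside is possibly one patient to replace, which 7.4 allows within the 4-6 week frame. The existing 4-day and one-month exclusions can stay as checks of acute state.
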